10.5 Priority order of study assessments

At certain time points, several assessments will be required at the same time. In these cases, the following ‘priority order’ will be followed:

- Resting 12-lead ECG
- Vital signs
- PK time-points (to be collected closest to the assigned time-point)

10.6 Adverse events

In order to avoid bias in eliciting AEs, subjects should be asked a non-leading question, such as “How are you feeling?” It is also important to question the subject in a non-leading way about changes in their health or concomitant medication usage since their last visit. All AEs will be recorded from the time the informed consent is signed until study exit, and are recorded on the appropriate pages in the eCRF and in source documents. Appropriate follow-up will be required for any adverse events ongoing at study exit.

Serious Adverse Events (SAEs) occurring up to 30 days after the last dose of study medication should be reported.

10.6.1 Definitions

Adverse Event (AE)

Any untoward medical occurrence in a subject or clinical trial subject administered a medicinal product and which does not necessarily have a causal relationship with this treatment. An adverse event (AE) can therefore be any unfavorable and unintended sign (including an abnormal laboratory finding, for example), symptom, or disease temporally associated with the use of a medicinal product, whether or not considered related to the medicinal product.

Adverse Drug Reaction (ADR)

All events considered being untoward and unintended responses to a medicinal product related to any dose should be considered adverse drug reactions. The definition covers also medication errors and uses outside what is foreseen in the protocol, including misuse and abuse of the product. The phrase “responses to a medicinal product” means that a causal relationship between

a medicinal product and an adverse event is at least a reasonable possibility, i.e., the relationship cannot be ruled out.

Serious Adverse Event (SAE)

An adverse event that at any dose:

- Results in death
- Is life-threatening (i.e. the subject was at risk of death at the time of the event; it does not refer to an event which hypothetically might have caused death if it was more severe)
- Requires inpatient hospitalization or prolongation of existing hospitalization (see explanation below)
- Results in persistent or significant disability/incapacity
- Is a congenital anomaly/birth defect
- Is considered to be an important medical event

Based upon medical and scientific judgment, important medical events that may not be immediately life-threatening, or result in death or hospitalization, but may jeopardize the subject or may require intervention to prevent one of the other outcomes listed in the definition above may be considered a serious adverse event.

Hospitalizations are defined as initial or prolonged admissions that include an overnight stay. Hospitalization or prolonged hospitalization for technical, practical or social reasons, in the absence of an adverse event is not an SAE.

An additional blood sample for the determination of NT-814 plasma levels should be taken in case of SAEs with reasonable possibility of relatedness to the study drug. The analysis of such PK samples will be conducted as soon as possible after the occurrence of the SAE.

Pregnancy

Pregnancy itself is not considered an AE. However, any pregnancy complication, spontaneous or elective abortion (for medical reasons), still birth, neonatal death, or congenital anomaly will be recorded as an AE or SAE.

Unexpected Adverse Drug Reaction

An adverse reaction, the nature or severity of which is not consistent with applicable product information (e.g., IB for an unapproved investigational medicinal product).

Reports which add significant information on the specificity, increase of occurrence, or severity of a known, already documented serious adverse reaction constitute unexpected events.

Suspected Unexpected Serious Adverse Reaction (SUSAR)

A serious adverse event that is suspected to be related to the administered medicinal product and the nature or severity of which is not consistent with applicable product information.

10.6.2 Assessment of causality

Severity

The severity (intensity) of each adverse event will be classified as:

- **Mild** Awareness of sign or symptom, but easily tolerated
- **Moderate** Sign or symptom causes discomfort, but does not interfere with normal activities
- **Severe** Sign or symptom of sufficient intensity to interfere with normal activities

Causality

An Investigator who is a qualified in medicine must make the determination of the relationship to study treatment for each AE.

The likely relationship of each adverse event to the medicinal product will be assessed according to the definitions below:

- Unrelated
- Possibly
- Probably
- Definitely

10.6.3 Serious Adverse Event reporting

Once the Investigator determines that an event meets the protocol definition of an SAE, the SAE will be reported to the Medical Monitor within 24 hours. Any follow-up information on a previously reported SAE will also be reported to the Medical Monitor within 24 hours.

If the Investigator does not have all information regarding an SAE, he/ she will not wait to receive additional information before notifying the Medical Monitor of the event and completing the appropriate data collection form. The Investigator will always provide a preliminary assessment of causality at the time of the initial report as described in Section 10.6.2.

The primary mechanism for reporting SAEs to the Medical Monitor will be a paper collection form.

The Medical Monitor contact details for SAE receipt can be found at the beginning of this protocol on the Sponsor/ Medical Monitor Contact Information page.

The contact details for reporting SAEs are as follows:

Fax transmission or 'scan & email' of the SAE form is the preferred method to transmit this information to the project contact for SAE receipt. In rare circumstances and in the absence of fax equipment, notification by telephone is acceptable, with a copy of the SAE data collection form sent by overnight mail. Initial notification via the telephone does not replace the need for

the Investigator to complete and sign the SAE data collection form within the designated reporting periods

All SUSARs, which occur with the investigational products within or outside the concerned clinical trial, if required, will be reported in compliance with the applicable regulatory authorities and Institutional Review Boards (IRBs). Fatal or life-threatening SUSARs must be reported within 7 calendar days and other SUSARs within 15 calendar days.

All investigators will receive a safety letter notifying them of relevant SUSAR reports. Each Investigator must then notify his or her Institutional Review Board (IRB) of the SAE as required by local regulatory authorities and in accordance with IRB policy. NeRRe will submit to the regulatory authorities all safety updates and periodic reports, as required by applicable regulatory requirements.

10.7 Safety review committee

After each cohort, the Safety Review Committee will evaluate the safety, tolerability and PK up to 14 days of dosing with NT-814 to determine escalation to the next dose in Cohorts 2 and 3 and the doses for Cohorts 4 and 5 (if applicable). Safety data to be reviewed will include, but is not limited to, AEs, vital signs, Holter monitoring data and available laboratory parameters. This review must comprise complete data up to Day 15 from a minimum of 14 subjects per cohort. The Safety Review Committee will be comprised of the Principal Investigator, Medical Monitor, appropriate Sponsor and CRO representatives.

Following review of data from a cohort of subjects, the timing of assessments and/or blood samples may be adjusted for subsequent cohorts. Additional assessment or sampling times may be added if indicated by the data; however, the maximum blood volume taken from each subject will not exceed 500 ml.

In the event that study stopping criteria have not been met, but the Safety Review Committee do not feel that it is appropriate to escalate to the next planned dose, the subsequent Cohort may be dosed at any of the previous dose levels, in order to confirm safety and PK data for this dose.

In the case of any safety concern or any ambiguous data, during any one of the cohorts, either individual subjects or the entire cohort may be unblinded to enable decision making. In this eventuality a separate un-blinded Safety Review Committee will be used to maintain the integrity of following cohorts. Details will be outlined in the Safety Review Committee Charter.

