Eligible subjects will be admitted to a Phase 1 Unit as an inpatient on the morning of Day -1 and will be fitted with and instructed on use of a sternal skin conductance monitor and Holter monitor which will be worn continuously until discharge from the clinic on Day 8; both the Holter monitor and sternal skin conductance monitor will be refitted on return to the Phase 1 Unit on Day 14. Routine safety monitoring will be carried out in a manner that will form the baseline for comparisons for the remainder of the study.

On Day 1, the subjects will be randomized in a 3:1 ratio to once daily (morning) doses of NT-814 or placebo, to be taken for a total of 14 days. Subjects will be monitored as an inpatient from Day -1 to Day 8 and will undergo blood draws for intensive PK sampling, safety monitoring and for impact on blood hormonal profiling as well as 24-hour skin conductance measurements and continuous completion of hot flash diaries.

Subjects will be discharged from the clinic on Day 8 without any monitoring devices, providing there are no safety concerns and will undergo dosing for a further 5 days as an outpatient. Subjects will be instructed to continue recording details of the hot flashes experienced, using the twice daily diary. They will be provided with the continuous daily diary and instructed to start completing this upon waking on the morning of Day 14 prior to admission to the clinic. They will be re-admitted to clinic on the morning of Day 14 for the final dose and undergo the same assessments with the same devices including Holter and skin conductance as Day 1. Subjects will be discharged following the 24-hour post Day 14 assessments (Day 15). Subjects will return to the clinic, as outpatients, for a single PK sample on the mornings of Days 16 and 17 (48 hours and 72 hours after the Day 14 dose respectively).

Throughout the study, subjects will be closely monitored for safety including assessments of AEs, 12-lead ECGs, atrial oxygen saturation using pulse oximetry, vital signs (sitting and standing BP, heart rate, oral body temperature, and respiration rate), clinical labs and physical examinations.

At the end of each Cohort a blinded review of PK and safety data from all subjects will be conducted by the Safety Review Committee (see Section 10.7) to confirm that it is safe to proceed to the next

dose. This review must comprise complete data up to Day 17 from a minimum of 14 subjects per cohort.

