9.9 Cohort and dose escalation stopping criteria

After each cohort a Safety Review Committee will review and assess all the available safety and PK study data from all of the cohorts to date in order to make a decision on the dose for the next cohort of subjects.

Data from a minimum of 14 subjects from the previous cohort must be reviewed before a decision to escalate can be taken.

The stopping criteria listed below apply to stopping during a cohort or at the end of a cohort during safety data review. Events that occur during the cohort will be passed onto the unblinded safety reviewers who will inform the study team of whether stopping criteria have been fulfilled and in such a case no other subjects will be enrolled. Subjects on treatment will be asked to stop dosing and if possible go through the early termination assessments.

1. One subject who has received NT-814 reports a serious adverse event which is considered at least possibly related to the NT-814
2. Two or more subjects, who have received NT-814, have QTc prolongation, defined as QTc > 500 ms for both Bazett and Fridericia corrections, or a prolongation from baseline of > 60 ms, confirmed (persistent for at least 5 min) during continuous ECG monitoring deemed to be at least possibly related to study drug (discovered at the end of the cohort during safety data review or on repeat ECGs taken during the study at the pre-determined time points or at the time of an AE)
3. Two or more subjects, who have received NT-814, have tachycardia, defined as resting supine heart rate > 125 beats per minute persisting for at least 10 minutes deemed to be unrelated to a hot flash episode and at least possibly related to study drug during continuous ECG monitoring (discovered at the end of the cohort during safety data review or on a repeat ECGs taken during the study at the pre-determined time points or at the time of an AE)
4. Two or more subjects, who have received NT-814, have symptomatic bradycardia, defined as resting supine heart rate < 45 beats per minute or asymptomatic bradycardia defined as resting supine heart rate < 30 beats per minute while awake persisting for at least 10 minutes during continuous ECG monitoring deemed to be at least possibly related to study drug (discovered at the end of the cohort during safety data review or on a repeat ECGs taken during the study at the pre-determined time points or at the time of an AE)

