- 4 On Days 1 and 14, 12-lead ECG pre-dose and at 0.5, 1, 1.5, 2.0, 2.5, 3.0, 4.0, 8.0, 12.0 and 24.0 hours (all +/- 15 mins). The same assessments schedule is required on Day -1, starting at a similar time to that planned for Days 1 and 14. Once daily ECG recordings will be made just prior to dosing (approx. 30 mins) on all other days (Days 3-8) during inpatient stays.
- 5 Subjects need to complete paper-diary for the 2 weeks prior to Baseline visit to ascertain eligibility. Subjects also to record number of times awoken during the night due to flashes (Night time awakening (NTA). On Days -1 to 7 and on Day 14 subjects to record the occurrence and severity of the flash (scale 1 to 3) in a continuous diary. Diary to be provided to subjects during screening and at discharge on Day 8 and subjects instructed to start completing it after waking on the mornings of Day -1 and 14 prior to admission and throughout the day and night. In the inpatient treatment part of the study, subjects also push a button on the skin conductance monitor when they sense a hot flash
- 6 Skin conductance and Holter monitors to be fitted on Day -1 (24 hours prior to the planned study drug administration on Day 1) and remain in place until after the 24 hour assessments are completed on Day 8 and then for 24-hours from pre-dose on Day 14 to discharge on Day 15.
- 7 Study drug will be administered in the morning from Day 1 to Day 14. Study medication will be dispensed to the subject on Day 8 for self-administration at home (for Days 9 to 13).
- 8 LH sampling every 60 mins from time 0 (pre-dose on Day 1 and Day 7) to 8 hrs. The same sampling schedule is required on Day -1, starting at a similar time to that planned for Days 1 and 7.
- 9 PK Sampling at Pre-dose; 0.5; 1.0; 1.5; 2.0; 2.5; 3.0; 4.0; 5.0; 6.0; 8.0; 12.0; 24.0 hours; 48.0, 72.0 hours after Day 14 only.
- 10 Pre-dose samples for PK and LH to be taken within 30 minutes prior to dose administration
- 11 Telephone follow up visit, unless deemed by the investigator that a clinic visit is more appropriate to follow up an adverse event
- 12 Where possible, all subjects who are withdrawn or withdraw from the study early will undergo the Early Termination Visit assessments.

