10.3 Pharmacokinetics

Blood samples for PK analysis will be collected at the following time points on Day 1 and Day 7:

Pre-dose; 0.5; 1.0; 1.5; 2.0; 2.5; 3.0; 4.0; 5.0; 6.0; 8.0; 12.0; 24.0 hours

On Day 14 blood samples will be taken for PK analysis at the following time points:

Pre-dose; 0.5; 1.0; 1.5; 2.0; 2.5; 3.0; 4.0; 5.0; 6.0; 8.0; 12.0; 24.0, 48.0, 72.0 hours

The pre-dose sample will be collected within 30 minutes prior to dose administration. On Days 1 and 7 the 24 hour PK sample must be taken prior to the dose of study medication the following morning.

Blood samples may be collected via a cannula or by direct venipuncture.

Pharmacokinetic samples will be collected as close to the nominal time point as possible. Allowable windows for PK sample collection relative to dosing (the dose at the start of the PK profile) will be as follows: ± 2 minutes up to and including 2 hours post-dose, ± 5 minutes up to and including 8 hours post-dose, ± 10 minutes up to and including 24 hours post-dose; ± 30 minutes up to and including 72 hours post-dose.

The visits on Days 16 and 17 must be scheduled to enable the samples to be taken at 48 and 72 hours, ± 30 minutes, relative to the final dose on Day 14.

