11.4 Study specific data analysis

At the end of each Cohort a blinded review of PK and safety data will be conducted by the Principal Investigator, Medical Monitor and Sponsor team to confirm whether it is considered safe to continue to the subsequent dose. Dose escalation will not occur if the exposure of NT-814 is predicted to exceed a geometric mean AUC of 20950 ng.h/mL (2-fold safety margin).

In the case of an ambiguous decision, all data may be unblinded to help with the dose escalation decisions.

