4.9 Pharmacokinetic Sampling Schedule

Blood samples for PK analysis will be collected at the following time points on Days 1, 7, and 14: predose, and 0.5, 1.0, 1.5, 2.0, 2.5, 3.0, 4.0, 5.0, 6.0, 8.0, 12.0, and 24.0 hours postdose. For Cohorts 3 onwards, additional samples will be collected at 48.0 and 72.0 hours after the Day 14 dose.

The predose sample will be collected within 30 minutes prior to dose administration.

Pharmacokinetic samples will be collected as close to the nominal time point as possible. Allowable windows for PK sample collection relative to dosing will be as follows: ± 2 minutes through 2 hours postdose, ± 5 minutes through 8 hours postdose, ± 10 minutes through 24 hours postdose and ± 30 minutes for the 48 and 72 hour postdose samples.

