Blood samples for PK analysis will be collected at the following time points on Day 1, Day 7 and Day 14: Pre-dose, 0.5, 1.0, 1.5, 2.0, 2.5, 3.0, 4.0, 5.0, 6.0, 8.0, 12.0, 24.0 hours. Additional sampling times of 48 and 72 hours will be collected following the Day 14 dose. The pre-dose sample will be collected within 30 minutes prior to dose administration.

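### The protocol gives two different data cut-offs, Day 15 and Day 17, for the same dose-escalation review

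*Protocol*

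**What the plan says.** Five places describe the review that must precede the next dose.

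- Protocol 8.4 (Study design) assigns it to the Safety Review Committee, points to Section 10.7, and states: "This review must comprise complete data up to Day 17 from a minimum of 14 subjects per cohort".
- SAP 4.1 (General) repeats that sentence, also with Day 17.
- Protocol 10.7 (Safety review committee) states: "This review must comprise complete data up to Day 15 from a minimum of 14 subjects per cohort".
- Protocol 9.9 (Cohort and dose escalation stopping criteria) keeps the subject minimum and gives no day: "Data from a minimum of 14 subjects from the previous cohort must be reviewed before a decision to escalate can be taken".
- Protocol 11.4 (Study specific data analysis) gives neither a day nor a minimum: "At the end of each Cohort a blinded review of PK and safety data will be conducted by the Principal Investigator", together with the Medical Monitor and the sponsor team.

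On what is scheduled between the two cut-offs, Protocol 10.3 says "The visits on Days 16 and 17 must be scheduled to enable the samples to be taken at 48 and 72 hours", and the Table 2 footnote on PK sampling lists the 48 h and "72.0 hours after Day 14 only" time points. Table 2 also schedules adverse event recording on Days 16 and 17. The PK SAP, section 3, agrees: "Additional sampling times of 48 and 72 hours will be collected following the Day 14 dose". SAP 4.9 is narrower: "For Cohorts 3 onwards, additional samples will be collected at 48.0 and 72.0 hours after the Day 14 dose".

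**The concern.** This rule fixes the least information the committee may hold before a new group of women receives a higher dose. Such a threshold needs a single value. With two, a team working from 10.7 can hold a review that is a protocol deviation under 8.4.

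A Day 15 review could go ahead without the two late PK samples and with one day of adverse event follow-up after the last dose. The protocol's background (5.5) notes that only one woman had been dosed before this study. Section 9.2 adds that the doses for Cohorts 4 and 5 will be set by PK modelling of the first three cohorts, up to 400 mg, and late concentrations could inform such a model.

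**Working it through.** No power or error-rate figure is involved. The check is a comparison of the texts, followed by a count of what falls between the two days.

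**1. The rules side by side**

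| Place | Data required up to | Minimum subjects |
|---|---|---|
| Protocol 8.4 | Day 17 | 14 |
| SAP 4.1 | Day 17 | 14 |
| Protocol 10.7 | Day 15 | 14 |
| Protocol 9.9 | not stated | 14 |
| Protocol 11.4 | not stated | not stated |

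**2. Is it the same review?** Yes. Section 8.4 names the committee and cross-refers to 10.7. Both sections cover PK as well as safety, so Day 15 cannot be read as a safety-only cut-off. No sentence ties either day to particular cohorts or gives one section precedence. Sections 9.9 and 11.4 name no day, so they neither contradict the others nor settle the matter.

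**3. PK samples between the cut-offs** (Protocol 10.3)

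- Day 1: 13 time points. Day 7: 13. Day 14: 13 + 2 = 15. Total: 13 + 13 + 15 = 41.
- Missing at Day 15: 2/15 = 13.3% of the Day 14 profile, and 2/41 = 4.9% of all PK time points.
- Over the 14 required subjects: 14 × 2 = 28 sample times at most, fewer if some have already passed Day 17. With 15 active and 5 placebo per cohort, 14 subjects include at least 14 − 5 = 9 on NT-814 and on average 14 × 15/20 = 10.5. The sample times from subjects on the drug are therefore 18 to 28, about 21 on average.

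**4. Follow-up after the last dose (Day 14)**

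- To Day 15: 1 day. To Day 17: 3 days. To the Day 21 call: 7 days.

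**5. What does not change.** The Day 14 AUC over 24 hours and Cmax, the Holter recordings and the Day 15 hormone samples are all collected by Day 15. The limit on predicted geometric mean AUC (20950 ng.h/mL, Section 9.9, criterion 11) can be assessed under either rule.

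**6. What the late samples could add.** As an illustration, PK SAP 8.1.2 requires the terminal-slope interval to span at least 1.5 half-lives. A profile ending at 24 h can support only half-lives below 24/1.5 = 16 h, and one ending at 72 h only those below 72/1.5 = 48 h. The documents give no half-life for the drug, and this rule governs the final analysis rather than the committee's review. The figures show relevance, not harm.

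**The case against.** The strongest reply is that both rules are floors and can be met together: a Day 17 review satisfies each of them, and a team reading the whole protocol would apply the stricter one. Other safeguards also exist. Section 9.9 has the committee assess whatever safety and PK data are available from all cohorts, so Day 16 and 17 results already in hand could not be set aside. Stopping criteria also apply during a cohort, and serious adverse events are reported within 24 hours. PK samples are shipped to Italy and analysed after each cohort, so a review exactly at Day 15 is unlikely, although the documents give no turnaround time. Subjects enrolled earlier will often have passed Day 17 by then. Finally, if SAP 4.9 is right that late samples start with Cohort 3, no extra PK data are at stake in the reviews after Cohorts 1 and 2.

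All of this stands as a limit on the consequence. It does not remove the conflict: Section 10.7 still permits what 8.4 forbids. The SAP 4.9 restriction cannot reconcile the two days either, because neither 8.4 nor 10.7 varies its cut-off by cohort, and the protocol and PK SAP section 3 put no cohort limit on the late samples. Adverse event recording on Days 16 and 17 is scheduled in Table 2 for every cohort.

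**Conclusion.** The contradiction is real and is in current text. Protocol 10.7 conflicts with Protocol 8.4 and SAP 4.1 on the minimum data for escalation. The gap is two days, two PK samples per subject where they are scheduled, and two days of adverse event recording. The effect on the escalation decision is probably small, because the exposure measure used for the AUC limit is complete by Day 15. It should still be corrected, since it is the minimum requirement before a higher dose.

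That Day 17 is the intended value is an inference. The current schedule has visits on Days 16 and 17, and the SAP version history says section 4.1 was revised for protocol version 4.0, without saying which sentence changed. This suggests that 10.7 was missed in the update but does not prove it.

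**What to change.** In Protocol 10.7, change Day 15 to Day 17. This alone removes the contradiction; 8.4 and SAP 4.1 stay as they are. It is also useful, though optional, to have 9.9 and 11.4 refer to the same rule: all data through Day 17 from 14 or more subjects, including the 48 h and 72 h PK samples where scheduled. The last two words are needed until SAP 4.9 and the protocol agree on which cohorts give those samples.

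**Cost.** At most 2 days per review.

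- Four cohorts, 3 decisions: 2 × 3 = 6 days.
- Five cohorts, 4 decisions: 2 × 4 = 8 days.
- Planned study period in the synopsis, 01-Aug-2016 to 31-Mar-2017: 242 days. 6/242 = 2.5% and 8/242 = 3.3%.

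These are upper bounds, since assay time may absorb part of the wait. If late samples are taken only from Cohort 3, the delay attributable to PK is 2 to 4 days (2/242 = 0.8% to 4/242 = 1.7%), and the rest buys adverse event follow-up only. No extra subjects, samples or unblinding are needed.
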